Business as usual

Business as usual will be explored as part of the internal pilot study. There is a paucity of good quality intensive interventions for young people who use drugs. An initial scoping review of services, both statutory and non-statutory, has identified several organisations who provide services for young people who use drugs. Avon and Wiltshire Mental Health Partnership Trust has a specialist young person's substance use service that offers brief interventions such as motivational interviewing and motivational enhancement therapy for those at a high level of severity. Sessions, lasting approximately 45-minutes are offered weekly over a period of 2-4 weeks. Bristol Drugs Project offers 1:1 and group support over a 12-week period. In Newport, Barod offer 1:1 support and peer group sessions over 6-week period addressing alcohol and

drug use, harm reduction and psychoeducation. Gwent Drug and Alcohol Service also offer some support to YP although most of their support is targeted at adults.

Young people who are referred to the Front Door of both Newport and Bristol for reasons that fit with the eligibility criteria of this bid and who are placed in the control group, will not be offered any therapeutic intervention akin to MDFT, BAU is provided by other services rather than Barnardo's so MDFT therapists will not be involved in delivering BAU. They and their family may receive Family Support help which focusses on basic parenting skills and confidence and a "light tough" intervention directly with the young person. This might involve them being referred to a youth work provision which is most likely to be activity based with the aim of diverting them into more positive, pro-social use of their time. For some young people, there may be access to mentoring support, though this is dependent on geography and capacity, not all areas of Newport or Bristol have mentoring support, and it is in demand. It is usually delivered by a youth worker or volunteer and aims to involve young people in more positive activities and, at times, supports them to access education or training opportunities. MDFT differs significantly from BAU.

Impact evaluation

Research questions or study objectives

Primary research question

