Compliance

We will assess adherence using the MDFT clinical portal, this assesses the dose and duration of interventions planned and delivered including the specific domains targeted at each session. A minimum dose of MDFT is defined as completion of the following metrics over a 6-month period.:

- Adolescent-only Sessions: 55% of total sessions being completed.
- Family Sessions: 30% of total sessions (includes the time within family sessions when therapist might have a little one on one time with youth or parent if needed).
- Parent/ carer-only sessions: 15% of total sessions (maybe with a single parent/ carer alone, and/ or time with the parenting team/ system together.

We plan on conducting a secondary analysis using a Complier Average Causal Effects (CACE) model using an instrumental variable framework. CACE analysis allows us to avoid bias by weighting the ITT treatment effect by compliance with the intervention or control treatment received, this provides an unbiased estimate of the role of compliance in the outcomes observed. By using different thresholds of compliance, a minimum threshold of 12 sessions over 4 months versus complete compliance, we can explore the nature of the relationship between compliance with the intervention and outcomes observed.

Analysis

Pilot study analysis

In the pilot study we will explore the distributional assumptions for each outcome measure and present descriptive statistics, either parametric or non-parametric overall, by allocated group and by stratification variables. We will estimate likely proportions of participants who are eligible, consent and followed up at 6 months. Each of these will be assessed against progression criteria detailed in appendix I (**PRQ1**, **PRQ2**).

We will conduct a descriptive analysis of outcomes including measures of central tendency and estimates of precision for continuous outcomes and proportions for categorical outcomes. Inferential analysis at the pilot stage will focus on the primary outcome and will involve a futility analysis using a fractional regression adjusted for stratification variables. This will allow us to confirm or revise our sample size calculation (**PRQ3, PRQ4**).

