The qualitative aspect of the work will involve the collection of narrative accounts from a range of individuals using semi-structured interviews. These will be collected from young people participating, carers and staff involved in the programme delivery and professionally associated with the young people. Professionals will be sampled purposefully from the different staff groups, and young people will also be purposefully sampled. Synthesis of these data sources will allow a detailed overview of the implementation and processes associated with successful delivery of the intervention.

Table 5: IPE methods overview

IPE Question	Data collection methods	Participants/ data sources (type, number)	Data analysis methods	Research questions addressed	Implementation/ logic model relevance
Fidelity/ adherence/ differentiation/ quality	Participant survey, therapeutic alliance, session data	400 participant surveys and TASC-r	Regression analysis	Quantification of the role fidelity, and quality plays in the outcomes observed	Better quality interventions that involve better alliance and communication between young people and practitioners are associated with better outcomes.
Compliance	Session planned and attended, outcome data	400 participant surveys, process database	Complier Average Causal Effect analysis	Estimation of the role compliance plays on observed outcomes at variable thresholds	Greater frequency of intervention is associated with better outcomes

	Factors associated with non- compliance	400 participant surveys, process database	Latent Class Analysis	Explore factors associated with non-compliance	Create targeted opportunities to reduce non-compliance and maximise acceptability.
Reach	Cohort Approach	Data on all young people referred to the service compared with data for those who consented	Logistic regression whether the model with intervention consent as the dependent outcome referred to the services		Identify any potential issues with accessibility.
	Qualitative interviews with service leads and key stakeholders	10 semi- structured interviews	Transcribing and inductive analysis to allow themes to emerge naturally	Identify any populations that experienced limited accessibility and the potential reasons for this.	Identify issues with accessibility and how these may be addressed

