Appendix II: Progression criteria from internal pilot

Project implementation

Area	Question	Assessment	Criteria	Rag rating
Therapist Recruitment	Have sufficient therapists been	Number of therapists recruited	7	>6 in post
	recruited			<6 >4 in post
				<4 in post
Therapist Training	Have sufficient therapists been	% of therapists certified	75%	>75%
	certified			60 – 74%
				<60%
Therapist Supervision	Do therapists attend planned supervision	% of therapist supervision sessions attended	75%	>75%
				60 – 74%
				<60%
Therapist Capacity	ls there sufficient capacity to provide MDFT Is there sufficient capacity to provide capacity Model of randomisation/ capacity		100%	100%
			90-99% increase number of therapists by 1	
				<90% increase number of therapists by required number
			80%	>80%

Dosage within 4-6 months 55% adolescent sessions 30% family sessions 15% parent alone sessions	Do participants comply with the minimal dose of MDFT	% participants receiving minimal dose		60-79% <60%
Eligible referrals	Are sufficient referrals eligible	% of eligible participants who consent	80%	>80% 50 - 79% <50%
Acceptability of adaptions	Are the adaptions to MDFT acceptable to therapists and participants	Review of adaptions	Adaption should be acceptable	Acceptable to some but not all revise adaption Not acceptable

Internal pilot evaluation

Area	Question	Assessment	Criteria	Rag rating
Participant recruitment	· ·	60	60	
				42-60
				<42
Evaluation attrition	aluation attrition Have sufficient % of participan participants been retained		90%	>90%
				70 – 89%

	retained at 6- months			<70%
Proportion with primary outcome	Have sufficient participants	% of participants completing primary	95%	>94%
recorded at month	provided a primary outcome	outcome		75 – 94%
				<75%%
Proportion with secondary outcome	Have sufficient participants	% of participants completing	80%	>80%
recorded at month 6	provided a secondary	secondary outcome		60 – 79%
	outcome			<60%
Analysable primary and secondary	secondary participants who providing usefull	providing usefull primary and secondary	80%	>80%
outcome data				60 – 79%
		outcomes		<60%
Randomisation	Are the groups allocated to MSFT and BAU of similar size	Difference in the proportion allocated to each group	2%	<2%
				3-5%
				>5%
Randomisation	Are the groups allocated to MSFT	Difference in the proportion allocated to each group by	5%	<5%
	and BAU of similar size by stratification			5-10%
stratific		stratification		>10%

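### Comparing the CACE at 12 sessions with the CACE at complete compliance cannot show how dose relates to outcome, because both are the same ITT effect divided by different attendance shares

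*Protocol*

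**What the plan says.** The Compliance section of the protocol announces a secondary analysis by a "Complier Average Causal Effects (CACE) model using an instrumental variable framework". It describes the method as "weighting the ITT treatment effect by compliance with the intervention or control treatment received" and says that this gives an unbiased estimate of the part that compliance plays. It then sets two cut-offs and a purpose: "By using different thresholds of compliance, a minimum threshold of 12 sessions over 4 months versus complete compliance", so that "we can explore the nature of the relationship between compliance with the intervention and outcomes observed".

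The compliance row of Table 5 repeats the plan ("Estimation of the role compliance plays on observed outcomes at variable thresholds"). In its logic-model column it gives the proposition "Greater frequency of intervention is associated with better outcomes".

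The Business as usual section says that young people in the control group "will not be offered any therapeutic intervention akin to MDFT", and the Risks table expects no contamination. The protocol states no exclusion restriction and gives no number of sessions for complete compliance.

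**The concern.** A CACE that uses randomisation as the instrument rescales the ITT effect. Moving the cut-off changes the divisor and leaves the numerator alone. The difference between the two planned estimates is therefore a fact about attendance, yet the protocol presents it as a way to learn how compliance relates to outcome.

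The stricter cut-off also strains the exclusion restriction, under which allocation may affect outcome only through the exposure as defined. At complete compliance, everyone who attends 12 or more sessions without completing counts as untreated, and any benefit they gain is credited to the completers.

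The Exploring Adaptation section says that the logic model will draw on quantitative analysis of adherence and dosage. A gradient produced by the divisor alone could enter it as support for more sessions.

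**Working it through.** **Inputs from the protocol.** ITT effect 0.27 SD, pre-post correlation 0.4, two-sided alpha 0.05, power 80%, 182 followed up per arm (Sample size calculations). Controls receive no MDFT (Business as usual; Risks).

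**Inputs assumed.** The protocol gives no expected share reaching 12 sessions (p_min) or completing (p_c). Appendix II sets an 80% pilot target, with a lower band starting at 60%, for the question "Do participants comply with the minimal dose of MDFT". That item is defined by a mix of session types and not by 12 sessions, so 0.80 and 0.60 are used here only as plausible values of p_min. For p_c the range is 0.20 to 0.60.

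**Step 1: the protocol's own figure.** Per arm, n = 2(1.96 + 0.842)²/0.27² × (1 − 0.4²) = 215.3 × 0.84 = 180.9, so 181 per arm and 362 in total, against 364 stated. Power at 182 per arm is 80.2%. The 0.27 is therefore the ITT effect on which the trial is sized.

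**Step 2: the estimator.** With no MDFT among controls, CACE(cut-off) = ITT / p(cut-off). Hence CACE(complete) / CACE(12) = p_min / p_c. The outcome has cancelled, and only attendance remains.

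| p_min | p_c | CACE at 12 sessions | CACE at complete | Ratio |
|---|---|---|---|---|
| 0.80 | 0.60 | 0.27/0.80 = 0.338 | 0.27/0.60 = 0.450 | 1.33 |
| 0.80 | 0.40 | 0.338 | 0.675 | 2.0 |
| 0.80 | 0.20 | 0.338 | 1.350 | 4.0 |
| 0.60 | 0.60 | 0.450 | 0.450 | 1.0 |
| 0.60 | 0.40 | 0.450 | 0.675 | 1.5 |
| 0.60 | 0.20 | 0.450 | 1.350 | 3.0 |

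**Step 3: does the comparison respond to the true dose-response?** A simulation used 364 participants, 2,000 replicates, p_min 0.80 and p_c 0.40.

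| True pattern | Mean CACE at 12 | Mean CACE at complete |
|---|---|---|
| All benefit reached at 12 sessions, none added after | 0.339 | 0.682 |
| Same benefit for everyone allocated MDFT | 0.334 | 0.673 |
| Completers benefit half as much as those reaching 12 only | 0.335 | 0.678 |
| No effect | 0.004 | 0.009 |

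In every replicate the stricter cut-off gave the larger magnitude. Flat and reversed dose-responses look alike.

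**Step 4: the bias at complete compliance.** Write d_c, d_m and d_b for the mean effects in completers, in those with 12 or more but incomplete sessions, and in those below 12. Then ITT/p_c = d_c + [(p_min − p_c)d_m + (1 − p_min)d_b]/p_c. In the first pattern d_c = d_m = 0.3375 and d_b = 0, so the estimate is 0.3375 + 0.40 × 0.3375/0.40 = 0.675, twice the true effect in completers. At the 12-session cut-off only d_b can cause bias: ITT/p_min = (effect in those reaching 12) + (1 − p_min)d_b/p_min. The session ranges in the Intervention section sum to 20 (8+4+4+4) to 50 (20+10+10+10), so those counted as untreated at complete compliance may have had substantial therapy.

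**Step 5: would sessions as a continuous exposure rescue it?** With allocation as the only instrument, two-stage least squares gives ITT / mean sessions. Suppose attendance is uniform on 0 to 40 (mean 20). If one session yields the whole 10-point gain, ITT = 10 × 40/41 = 9.76 points and the slope is 9.76/20 = 0.49 points per session. If the gain is truly 0.5 points per session, ITT = 10 and the slope is 0.50. The two cannot be told apart.

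**The case against.** The best defence is that this is a secondary, exploratory analysis beside an ITT primary. The protocol says only that it will explore a relationship. The Exploratory analysis section and the fidelity part of the process evaluation also plan regressions on adherence. The 12-session cut-off has a rationale, since Appendix I treats it as the minimum dosage, and the exclusion restriction fails only if attendance below the cut-off has some effect.

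Much of this stands, and it limits what can be said. A reader might infer that the protocol commits to reporting a rising CACE as dose-response. It does not: the Table 5 sentence is a logic-model proposition written beforehand, not a rule for reading results. A reader might also infer that the estimate must always grow. It does not: a zero ITT effect stays near zero, a harmful one becomes more negative, and equal attendance shares give equal estimates. Nor do the documents support one large figure for the distortion, because they give neither attendance share. No passage ties the CACE to commissioning.

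The defence does not restore the comparison. Calling it exploratory does not help when the ratio contains no outcome data, and the planned adherence regressions are observational analyses that leave this one as it is.

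**Conclusion.** The concern holds in this form. The cross-threshold comparison is uninformative about dose, and the claim of an unbiased result is wrong without stated assumptions. What the method estimates is an effect among compliers, valid only if allocation acts solely through the defined exposure.

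The direction rests on three conditions: no MDFT in controls, a non-zero ITT effect, and fewer completers than people reaching 12 sessions. The size rests on assumed attendance. The ratio runs from 1.33 to 4.0 when 80% reach 12 sessions and 60% down to 20% complete. Bias is the larger worry at complete compliance and smaller at 12 sessions. The fault lies in a secondary analysis and should be corrected, but it does not touch the primary result.

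**What to change.** - Pre-specify one CACE with exposure defined as attending any MDFT session, and state the exclusion restriction. This is the definition under which it is most credible.
- Keep the 12-session CACE, if wanted, as a sensitivity analysis with its assumption about lower attendance stated.
- Delete the inference drawn from comparing cut-offs, and replace the claim of an unbiased result with an effect among compliers under stated assumptions.
- Amend the compliance row of Table 5 so that this CACE does not inform the proposition about frequency and outcome.
- Do not substitute two-stage least squares on number of sessions as evidence of dose-response. It assumes linearity and cannot test it. Label any dose analysis as observational or assumption-dependent.
- Reconcile the definitions of minimum dose. The Compliance section gives both a session mix over 6 months and 12 sessions in 4 months, Appendix II uses the mix, and complete compliance is undefined.

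The cost is wording only. The clinical portal already records the dose and duration delivered, so no new data are needed. The price is that the trial makes no randomisation-based claim about dose-response.

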- ERQ13 To conduct a latent class mediation analysis to explore how the volume of violent offences is mediated by the frequency and type of substance used at 6 and 12 months.

Part of this work will be to examine the potential impact of both UK and region-specific issues that may be linked to race, ethnicity, sex, socioeconomic factors and other considerations that may arise which are connected to EDI.

Internal pilot study

Prior to embarking on the efficacy study an internal pilot study will be undertaken. The aim of the internal pilot study is to explore whether it is feasible to deliver MDFT in the UK context and establish key parameters to incorporate into the design of the efficacy study. Progression criteria are detailed in appendix II and the study will be conducted between September 2025 with a transition decision in June 2026.

In the pilot study we will recruit 60 participants, 30 in each arm, across the 2 sites. This will allow for exploration of key parameters needed to confirm sample size calculation for the efficacy study. It is sufficient to allow estimation of two-sided 95% CIs around the proportions of eligible, consenting, adhering and followed up at month 6 in each arm of the study with half-widths less than 0.15. It meets the 30 per group recommended by Lancaster et al (Lancaster et al., 2004) for estimating the SE of a primary outcome with sufficient precision, including accounting for any variation across site, where 12 participants per arm per site is recommended.

Objectives for the internal pilot trial

- **PRQ1** To conduct a prospective, two-arm, individually randomised RCT to pilot study outcomes and methods and establish the parameters for the conduct of efficacy evaluation.
- **PRQ2** To assess whether progression criteria have been met and develop an appropriately powered efficacy protocol.
- **PRQ3** To confirm the pre- post-test correlation on the primary outcome, percent days abstinent from alcohol and/or drugs to incorporate into a sample size calculation.
- **PRQ4** To estimate an estimate of potential effect for the primary outcome for inclusion in a sample size calculation.
- PRQ5 To explore the relationship between the use of alcohol and specific drugs and violent offending. This will be achieved through an analysis of existing datasets; Reframe and RISKIT-CJS, with a confirmatory analysis conducted on the pilot data at the time of transition.

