Data from the internal pilot and efficacy study will be combined and analysed blind to group allocation. The efficacy analysis will follow CONSORT guidelines. The primary outcome is fractional, a proportion constrained by 0 or 1. The analysis will be conducted using an analysis by intention to treat and will include all available data to maintain participants as members of their allocated group, irrespective of what intervention was received, this provides an unbiased estimate of effect. To adjust for potential bias from recruiting participants to the pilot or efficacy stage, we will use an individual patient data meta-analysis, entering a dichotomous pilot/efficacy variable into the model as a fixed effect. Differences between the groups will be presented as marginal means and their associated 95% confidence intervals. If the missing primary outcome data exceeds 10% sensitivity analyses will be performed using a pattern mixture approach and multiple imputation to compare the sensitivity of conclusions to varying assumptions about the missing data, particularly whether data is missing at random (MAR) or missing not at random (MNAR) this allows for an assessment of both random and systemic bias.

Secondary outcomes will be assessed in a similar way by establishing diagnostic plots to identify the most appropriate regression approach, including stratification factors and baseline covariates within a multi-level model.

The primary end point is 6 months post-randomisation. This will allow an assessment of impact for short term outcomes. In order to explore whether effects are sustained over time and assess impact on longer term outcomes a secondary analysis will be conducted at 12-months post randomisation.

Exploratory analysis

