Young people may not want to consent to being part of study resulting in lack of numbers for the evaluation	Young people will have access to a clear information sheet highlighting the need to evaluate a new service. Information will be reviewed by a young person's advisory group who will provide input on how best to engage young people in the research. Our experience of other studies with similar populations is that many young people are motivated by altruism, the opportunity to contribute to services that will help others in a similar position in the future.

The potential that young people, therapists and researchers experience negative impacts of participating in the study.	All staff and researchers have access to supervision to raise issues relating to the trial. We will implement a reporting system to allow all staff, young people and their carers and researchers to highlight any potential adverse events and, if needed, seek support. We will implement an independent DMEC to review adverse and iatrogenic effects as they arise and if they believe these are directly attributable to the trial and severe in nature, they will raise the potential of stopping the trial with the research team and funder.
Families may be resistant to participating in the trial.	We have extensive experience of including marginalised populations in evaluations. The pilot study will explore qualitatively barriers to participation. All information about the trial will be available in advance of consent and potential participants provided an opportunity to discuss participation. Consent will be based on the consent of the young person rather than the family and early work in delivering MDFT identifies the most appropriate family members to be involved in the delivery of MDFT.
Young people may exhibit demoralisation if randomised to BAU rather than the MDFT intervention.	Clear information to participants that the study involves a state of equipoise, that at this stage we have no evidence that MDFT is better than BAU and this is what is being tested. Disengagement and 'faking bad' are key signs of resentful demoralisation and both concepts will be explored qualitatively with young people.

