Sites may drop out of the study due to changes locally related to financial issues or leadership.	All sites have a track record of commitment to the delivery of services and an understanding of research. Senior sign off has been secured at all sites and commitment made to deliver the research as planned.
Imposition of COVID, or similar, restrictions	Both the delivery team and research team have contingency plans for remote working.
Poor quality delivery of MDFT	Fidelity and quality assurance are monitored throughout the study through the MDFT portal. Therapists are supervised both on-site and by staff from MDFT international. Regular

	reports relating to fidelity on the part of the therapist, adherence on the part of participants and quality assurance are made available and reviewed. Issues can be identified quickly and remedial action taken.
Participants do not complete questionnaires because they are too long	The outcome battery has been used in similar populations and takes on average 15 minutes to complete at baseline and 25 minutes at follow up. Response from other studies suggest burden will not be an issue.

Timeline

05/25 - 09/25: Adapt MDFT for delivery in UK, trial set-up, ethics, registration, recruitment of supervisors and therapists.

09/25 – 12/25: Conduct internal pilot with 60 participants recruited.

06/26: Evaluate transition criteria and submit transition report form.

07/26 - 05/27: Recruit 340 to efficacy study.

01/27 – 11/27: Conduct efficacy 6-month follow-up.

07/27 – 05/28: Conduct efficacy 12-month follow-up.

06/28: Analyse results.

09/28: Submit final report

Bibliography

- BALDWIN, S. A., CHRISTIAN, S., BERKELJON, A. & SHADISH, W. R. 2012. The effects of family therapies for adolescent delinquency and substance abuse: a meta-analysis. *J Marital Fam Ther*, 38, 281-304.
- BLACK, C. 2020. review of Drugs evidence relating to drug use, supply and effects, including current trends and future risks. London: HMSO.

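### At the pilot look the evaluation team gets every outcome by arm and a between-arm futility result, with no limit on who sees them, while the trial still has to recruit and follow up

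*Protocol*

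**What the plan says.** Under Analysis, Pilot study analysis, the team will "explore the distributional assumptions for each outcome measure" and "present descriptive statistics, either parametric or non-parametric overall, by allocated group and by stratification variables". The next paragraph adds inference on the primary outcome, which "will involve a futility analysis using a fractional regression adjusted for stratification variables". Its stated use is to confirm or change the sample size. PRQ4 (Objectives for the internal pilot trial) has the same purpose: "To estimate an estimate of potential effect for the primary outcome for inclusion in a sample size calculation". PRQ2 has the team develop the efficacy protocol from the pilot.

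On size and timing: "In the pilot study we will recruit 60 participants, 30 in each arm". The Timeline has "06/26: Evaluate transition criteria and submit transition report form", followed by recruitment of the other 340 from July 2026 to May 2027. The sample size section instead describes uninterrupted recruitment from September 2025 to January 2027.

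Efficacy study analysis then states: "Data from the internal pilot and efficacy study will be combined and analysed blind to group allocation". Participants and site staff are not blinded, while follow-up researchers are (Randomisation; Figure 3). The primary outcome is an interviewer-led calendar of self-reported use (Primary outcome). The Risks table provides an independent DMEC, with a remit of adverse and iatrogenic effects. No section confines the pilot's by-arm results to particular people or says that arms are coded at that stage.

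**The concern.** The pilot is internal: its participants are part of the confirmatory sample. Comparative outcome results would be produced by and for the team that goes on to run the trial, with most of the recruitment and follow-up still to come.

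A between-arm result known to the team can influence how equipoise is conveyed and how self-reported outcomes are elicited. It can also influence design choices still open at that moment, such as whether particular substances become the target of the efficacy trial (PRQ5) or which outcome assessments are kept (PRQ6). Because allocation is open, few other safeguards remain. The Risks table relies on telling participants that "at this stage we have no evidence that MDFT is better than BAU" to limit demoralisation in the BAU arm, so neutral presentation matters here.

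Disclosure cannot be undone, and the pilot estimate is so noisy that any influence could run in either direction.

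**Working it through.** **1. Inputs.** 60 pilot participants, 30 per arm (Internal pilot study); 400 in total, 10% loss, effect size 0.27, pre-post correlation 0.4, 364 followed up (Sample size calculations); 340 recruited after the report (Timeline).

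**2. The plan's own figure.** n per arm = 2(1.96 + 0.8416)²(1 − 0.4²)/0.27² = 2 × 7.849 × 0.84/0.0729 ≈ 181, or 362 in total against the stated 364. The design effect and correlation are therefore read correctly. The unadjusted total of 480 does not come out the same way (216 per arm, 432 in total), but nothing here depends on it.

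**3. What lies before and after the look.**
- Timeline schedule: 60/400 = 15% randomised; 340/400 = 85% still to recruit.
- Continuous schedule: 7 of the 17 recruitment months (July 2026 to January 2027) follow the report.
- Pilot recruits enter from September to December 2025, so their month-12 assessments fall from September to December 2026, after the report on either schedule.
- Primary outcome data in hand: 30 × 0.9 = 27 per arm; 54/364 = 15%.

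**4. Precision of the pilot comparison.** The descriptive tables are unadjusted, and the futility regression adjusts for stratification variables only, so the baseline covariate gives no gain in precision. By normal approximation:
- SE(d) = √(2/27) = 0.272; 95% half-width 1.96 × 0.272 = 0.53.
- No true effect: 0.27/0.272 = 0.992, so P(|d| ≥ 0.27) = 2 × Φ(−0.992) = 0.32.
- True d = 0.27: P(estimate ≤ 0) = Φ(−0.992) = 0.16.
- Power for d = 0.27: about 17%.

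**5. Range.** One stratification variable is substance use severity, which may explain some of the outcome variance. The protocol does not say how much. If it were worth as much as a correlation of 0.4, SE = 0.272 × √0.84 = 0.249, and the two probabilities become 0.28 and 0.14. The conclusion is the same across this range.

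**6. What the progression decision needs.** Appendix II covers therapist recruitment, certification, supervision and capacity; dose; consent; acceptability; participant recruitment; retention; completeness; and balance of allocation. No criterion compares outcomes between arms.

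**The case against.** Several stronger readings are tempting, and the documents do not support them.

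- **The funder sees results by arm.** A reader might infer this from the transition report, but the Timeline names neither its recipient nor any by-arm content.
- **The blind analysis is contradicted, or is void for 15% of the sample.** The statement concerns blinding to allocation. Coded arms could satisfy it, and aggregate summaries reveal no individual's arm. It is a tension only.
- **Follow-up researchers are unblinded.** Aggregate results do not tell an assessor which arm a participant is in.
- **Referrers, intake staff or participants learn the result.** No section sends it to them. Allocation is concealed and independent, so a shift in referrals could change case mix but not balance between arms.
- **The equipoise statement becomes untrue.** A pilot with a half-width of 0.53 would rarely be evidence either way.

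Two further objections are fair. On the Timeline the report falls in a planned recruitment gap, so recruitment resumes after the look rather than running through it. And the calculation measures imprecision; the documents give no basis for sizing bias from disclosure.

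The strongest objection is that access to interim results is usually set in an SAP or DMEC charter, so silence is no fault. That would hold if the protocol were merely silent. But it states that outcomes are presented by arm and that the between-arm result is used to reconsider the sample size and design. The team's own sight of the effect follows from that text.

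**Conclusion.** The concern holds in limited form. The protocol commits the evaluation team to by-arm results on every outcome and a between-arm futility result, with 85% of recruitment still ahead on the Timeline schedule. On either schedule, recruitment and assessor-blind follow-up continue after the look. The same data, 15% of the sample, re-enter the final analysis, and no access limit is stated.

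The comparison is too imprecise to guide decisions: roughly a one in three chance of a difference as large as the design effect when there is none, and one in six of zero or the wrong direction when the design effect is true. These figures assume 10% loss, equal arms and a normal approximation to a fractional outcome.

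The change should be made before the June 2026 report. It is a weakness in how interim results are handled, not proof that the final estimate will be biased.

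**What to change.** - **Pilot study analysis.** Limit by-arm reporting, to the team and in the transition report, to feasibility items: allocation, retention, completeness and dose. Report outcome distributions, standard deviations, missingness and the pre-post correlation (PRQ3) pooled over arms, and base any sample size check on these.
- **Futility analysis and PRQ4.** Moving the descriptive tables alone would leave these two routes to the same effect open. Confine by-arm outcome tables, the futility result and any effect estimate to the DMEC, which returns only a recommendation. Amend PRQ4 to match.
- **DMEC remit (Risks table).** Extend it beyond adverse and iatrogenic effects to cover these results.

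Cost: protocol wording and a slightly wider DMEC remit. The team and funder would see no preliminary effect before the final analysis. The progression decision is unaffected.
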